#### 3.2 Secondary Objectives

The secondary research objectives used to address the main aim of the study are:

- Validation of a 3D movement analysis protocol for measuring upper limb function in children with shoulder instability.
- Obtain new data on muscle activity and movement patterns of children with and without shoulder instability
- Categorising clinical presentations of instability and identification of important factors for recurrent instability

This is not an experimental study and so there is not a single/primary outcome measure. The following outcomes will be derived from this study

*For the single movement analysis session:*

- **Kinematic** variables related to the movement tasks, for example
  - joint angles (degrees)
  - displacement (position, speed and associated derivatives)
- **Kinetic** variables related to the movement tasks, for example
  - forces/ strength (n, kg/force)
- **Muscle activity patterns** related to the movement tasks, for example
  - Surface electromyography (sEMG) (mv)

*For the follow up outcomes:*

- Number of recurrent episodes of instability

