### 8.3 Statistical analysis plan

The aim of this study is to identify factors responsible for recurrent shoulder instability in children. To meet the main aim, the following objectives, need to be met. The methods of analysis used to meet the study objectives have been reported below.

The analysis of measurement units will inform the main study objective and secondary objectives.

- **Kinematic** data such as joint angles and displacements – average range of movement values, as well as absolute minimum and maximum values will be reported for all functional tasks. For comparison purposes, descriptive statistics will be used to report the group behaviours and variability including means and standard deviations.
- **Kinetics** - force/strength – The range of force and strength values, as well as absolute minimum and maximum values will be reported for all functional tasks. For comparison purposes, descriptive statistics will be used to report the group behaviours and variability
- **Muscle activity patterns** - muscle activity (absence or presence), timing of muscle onset, percentage of maximum contraction and time of peak intensity will be used. This methodology is consistent with previously published research and is used for informing clinical decision making processes

The secondary research objectives used to address the main aim of the study are:

1. Validation of a 3D movement analysis protocol for measuring upper limb function in children with shoulder instability.
  - i) Individual variability (associated with of the measurement units outlined above) will be determined using the coefficient of variation for all data.
  - ii) The reliability and error associated with the protocol will be determined using the standard error of measurement for the measurement units outlined above. The reliability of the protocol will be determined through a sensitivity analysis investigating what effect perturbation of the virtual markers has on the outputs of the biomechanical model e.g. kinematics, position of the humerus
2. Obtain new data on muscle activity and movement patterns of children with and without shoulder instability
  - i) The method of analysis outlined above will inform this objective
3. Categorising clinical presentations of instability and identification of important factors for recurrent instability

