### **Measurement burden**

In order to minimise the measurement burden on all participants and ensure the aims of the study are met, our study design has been developed following input from a Public Involvement and Engagement

(PPIE) group, an additional 7 children of appropriate age groups outside of the PPIE and clinicians who routinely work with children with shoulder instability.

A primary aim of our study is to test the reliability and variability of a measurement analysis protocol in children with shoulder instability and age-matched controls. To minimize the measurement burden on children and their parent/carer/guardian, only a single study site visit, lasting a maximum of 2 hours 30 minutes, is required. Reliability will be determined by a sensitivity analysis in which we will virtually perturbate the markers post data collection. This has been selected to minimise the measurement burden of multiple visits for children with shoulder instability and the age matched controls. For children with shoulder instability this will also minimise the variability which may arise as a result of the natural recovery process over time and confound our results. The measurement protocol has been designed after consultation with different children of appropriate age groups, clinicians and the scientific literature.

Where possible, we will additionally try and accommodate measurement sessions outside of school hours for both groups to limit any school/lesson absences.

Diaries and monthly telephone calls (lasting up to 12 months), have been selected to ensure accurate recordings of the events and minimise recall bias. We have received input re the follow up study processes and diaries from the Public Involvement and Engagement group and additional children of appropriate age groups. We do not anticipate that participants will have a large number of instability episodes and so the measurement burden for recording will be minimal. Additionally, participants will only be asked to record when an episode happens.

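### The plan calls an assumed-input marker perturbation the protocol's reliability, and promises an SEM with no estimator that one visit can make within-session only; neither limit is stated

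*Combined protocol and SAP*

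**What the plan says.** Validating the movement analysis protocol is a secondary objective in sections 3.2 and 8.3: "Validation of a 3D movement analysis protocol for measuring upper limb function in children with shoulder instability". The Measurement burden text in section 11 ranks the same work higher: "A primary aim of our study is to test the reliability and variability of a measurement analysis protocol".

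Objective 1(ii) in section 8.3 has two sentences. The first is "The reliability and error associated with the protocol will be determined using the standard error of measurement for the measurement units outlined above". The second is "The reliability of the protocol will be determined through a sensitivity analysis investigating what effect perturbation of the virtual markers has on the outputs", and it concerns the outputs of the biomechanical model. Section 11 repeats it: "Reliability will be determined by a sensitivity analysis in which we will virtually perturbate the markers post data collection". Neither place gives a size, direction, distribution or source for the perturbation.

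The measurement units that the SEM is to cover include force and strength, and the EMG summaries: "muscle activity (absence or presence), timing of muscle onset, percentage of maximum contraction and time of peak intensity will be used". The first of these summaries is binary.

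Sections 4 and 11 specify a single site visit. Section 7.6.1 describes one sequence of landmark mark-up, sensor placement, cluster placement and pointer calibration. Section 11 justifies the single visit by burden on families and by natural recovery between visits. It does not say what a single visit leaves unmeasured.

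Section 8.1 attributes the lack of a power calculation to the SEM being unknown, ties the SEM to the minimally important difference, and promises population values of SEM in both groups for use in later power calculations.

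**The concern.** Two different quantities are presented as the protocol's reliability, and neither is what a reader would take that to mean.

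The perturbation size is chosen by the analyst, so the analysis answers a conditional question: if landmarks were misplaced by this much, how far would the model outputs move? It does not show how far landmarks are in fact misplaced in these children. It also has no bearing on outcomes that do not use virtual markers, such as grip strength and EMG.

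The SEM has no stated estimator or unit, and an SEM is not a natural summary for a yes/no outcome. If it is taken from the repetitions, it contains only what varies within one session. Palpating again, re-siting sensors, recalibrating or testing on another day would add error that the study cannot see. Section 8.1 offers the SEM to future studies without that qualification, so the wrong label would travel with the number.

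**Working it through.** The plan states no SEM, reliability figure or perturbation size, so there is nothing to reproduce. The check asks what the design can estimate.

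**Inputs.** 15 children per group (8.1); one visit (4, 11); one placement sequence (7.6.1). Maximum repetitions are 3 per side for grip (7.7.1), 2 sets of 6 for physiological and functional tasks (7.7.2), and 2 sets of 3 for loaded tasks (7.7.2, 7.7.4).

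**1. Re-application error.** Write a reading as child + application + set + residual. With one application per child, the application term has 15 × (1 − 1) = 0 degrees of freedom and cannot be separated from the child term. In a simulation of 15 children with 12 repetitions and a within-session SD of 1, the estimated SEM stayed at 1.00 whether the true single-repetition SEM was 1.00, 1.41 or 2.24.

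**2. Size of the omission, same unit.** Let f be the share of single-repetition error variance that is re-application or between-session. The documents give no value, so f is an assumption. Within-session SEM ÷ total SEM, both for one repetition, is √(1 − f):

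| f | ratio | shortfall |
|---|---|---|
| 0.06 | 0.970 | 3% |
| 0.25 | 0.866 | 13% |
| 0.50 | 0.707 | 29% |
| 0.75 | 0.500 | 50% |

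**3. One repetition or a child's mean.** Let s be the share of within-session variance that lies between sets (assumed 0 to 0.5), with k repetitions in each of 2 sets. The within-session SEM of a child's mean, relative to that of one repetition, is √(s/2 + (1 − s)/(2k)).
- 2×6 tasks: √(1/12) = 0.29 at s = 0; √(0.25 + 0.5/12) = 0.54 at s = 0.5.
- 2×3 tasks: √(1/6) = 0.41 at s = 0; √(0.25 + 0.5/6) = 0.58 at s = 0.5.

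This ambiguity needs no assumption about re-application.

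**4. Mixed units.** For a 2×6 task with total single-repetition error variance 1, the single-repetition within-session SEM divided by the full error of a child's mean is √[(1 − f)/(f + (1 − f)q)], with q = s/2 + (1 − s)/12.
- f = 0.06: √(0.94/0.138) = 2.6 at s = 0; √(0.94/0.334) = 1.7 at s = 0.5.
- f = 0.25: 1.5 down to 1.3.
- f = 0.50: 0.96 down to 0.88.
- f = 0.75: 0.57 down to 0.55.

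The direction therefore reverses at small f when units are mixed.

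**5. What can be estimated well.** Approximate 95% limits for the single-repetition within-session SEM, as multiples of the estimate, are √(df/χ²), per group and at maximum repetitions:
- Grip, per limb: df = 15 × 2 = 30, 0.80 to 1.34.
- 2×3 tasks: Satterthwaite df 67.5 at s = 0 and 31.8 at s = 0.5, giving 0.86 to 1.20 and 0.80 to 1.32.
- 2×6 tasks: df 154.3 and 41.9, giving 0.90 to 1.13 and 0.82 to 1.27.

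The repetition counts are upper limits in the protocol, so these intervals are best cases.

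**The case against.** The strongest reply is that the choice is deliberate and open. Section 11 says that reliability will come from virtual perturbation, both places call it a sensitivity analysis, and the reasons for avoiding a second visit are sound. Perturbation also addresses, by modelling, one part of re-application error: landmark location. All of this stands, and the single visit should be kept. But explaining why something was not measured is different from saying that it was not measured, and section 8.1 still promises the SEM without qualification.

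A second reply is that the harm lies downstream and its size is assumed. That is also fair. No group comparison or clustering in section 8.3 uses the SEM, so those results are unaffected.

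Sections 10.1 and 11 mention a first assessment, which might hint at a repeat. No second one is described.

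Four stronger readings are tempting, and the documents do not support them:
- That the within-session SEM is too small on any comparison. This holds only for the same unit. Section 8.3 plans average range-of-movement values, and set against the full error of a 2×6 child mean the single-repetition SEM could be too large (step 4).
- That the SEM would serve as the noise term in a later sample size. Section 8.1 links it to the target difference.
- That the SEM is itself to be derived from the perturbation. It is promised for all units, and moving virtual markers cannot yield one for grip or EMG; two separate analyses is the natural reading.
- That the coefficient of variation in objective 1(i), which "will be determined using the coefficient of variation for all data", is a separate conflict. It is assigned to individual variability and the SEM to reliability and error; what is missing is again the estimator.

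**Conclusion.** The plan is wrong as written on this point, and the repair is modest. Followed literally, it would report an assumed-input sensitivity result as reliability and a within-session SEM as the protocol's SEM, and it would attempt an SEM for a binary outcome. That re-application error is inestimable follows from the design, given the single placement sequence described.

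The size of the missing part is unknown. Over an assumed 6% to 75% share of single-repetition error variance, the single-repetition within-session SEM is 3% to 50% below the total for the same unit; at the low end this is trivial. The unstated unit alone changes the within-session SEM to between 0.29 and 0.58 of its single-repetition value for the movement tasks, assuming that 0% to 50% of within-session variance lies between sets.

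The data remain usable, and the within-session SEM can be estimated with useful precision from the planned repetitions. Section 8.1 may keep its link between SEM and a target difference, but a later two-group power calculation also needs the between-child SD. Section 8.3 already plans group SDs for kinematics: "report the group behaviours and variability including means and standard deviations".

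**What to change.** No second visit and no new data are needed.

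1. **Section 8.3, objective 1(ii).** Define a within-session SEM for continuous outcomes, by group, with a 95% confidence interval. Use child, set within child and residual for the 2×6 and 2×3 tasks. Use child and residual, per limb, for grip, since one repetition per set cannot separate set from residual. State whether the SEM refers to one repetition or the child's mean, matching how the outcome is reported. Name key outcomes first: the full EMG set alone is 10 muscles × 7 tasks × 3 continuous measures = 210 SEMs per group. For presence or absence of muscle activity, report within-child agreement across repetitions instead.
2. **Sections 8.3 and 11.** Call the perturbation work *sensitivity of model outputs to landmark error*. Fix the perturbation sizes and their source in advance. Do not report it as observed reliability or as the SEM.
3. **Limits.** State that re-application and between-session error are not measured, so the within-session SEM omits them and is expected to understate total error for the same unit (repetition against repetition, or mean against mean). Add that a single-repetition SEM should not be compared with the error of a child's mean.
4. **Section 8.1.** Limit the promised estimate to the within-session SEM, and add that between-child SDs will be reported with confidence intervals for future power calculations.

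Aligning the rank given to reliability in section 11 with the secondary objective in section 3.2 is optional tidying.

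The cost is protocol and SAP wording, some extra scripted reporting, and a narrower validation claim.

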## STUDY SUMMARY

Trial/Study* Title	Shoulder instability in children: understanding muscle activity and movement pattern differences	
Internal Ref. Number (or short title)	Shoulder instability in children: muscle activity and movement v2.0	
Trial/Study* Design	Cohort observation Cross-sectional study	
Trial Intervention (where applicable)	N/A	
Trial/Study* Participants	15 children (aged between 8 and 18) with shoulder instability 15 age matched controls	
Planned Sample Size	30 participants	
Treatment duration	2 hours 30 minutes maximum	
Follow up duration	12 months	
Planned Trial Period	24 months	
	Objectives	Outcome Measures
Primary	*	
Secondary		

\* This is not an experimental study and so there is not a single/primary outcome measure. The following outcomes will be derived from this study

[figure not shown]
*For the single movement analysis session:*

- **Kinematic** variables related to the movement tasks, for example
  - joint angles (degrees)
  - displacement (position, speed and associated derivatives)
- **Kinetic** variables related to the movement tasks, for example
  - forces/ strength (n, kg/force)
- **Muscle activity patterns** related to the movement tasks, for example
  - Surface electromyography (sEMG) (mv)

*For the follow up outcomes:*

- Number of recurrent episodes of instability

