### 3 OBJECTIVES AND OUTCOME MEASURES/ENDPOINTS

#### 3.1 Primary objective

- The primary objective of this study is to identify factors responsible for recurrent shoulder instability in children.

In order to meet the main objective of this study, a series of secondary objectives need to be met.

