## **7.8 Follow up for recurrent instability**

Following the movement analysis session, participants will be provided with a diary to record and further episodes of instability as per (appendix). Provided with information and guidance on how to complete the diary. Participants in both groups will additionally be followed up on a monthly basis via a telephone call for up to 12 months to record the number of instability episodes experienced. Monthly follow ups have been selected to ensure accurate recording of instability episodes and facilitation of diary recordings.

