  - i) data from study objective 2 will be evaluated to identify features i.e. movement or muscle activity patterns, which may be used to categorise clinical presentations of shoulder instability. An appropriate clustering/categorisation method will be selected once the characteristics of the dataset has been established

if we get a large enough sample size of participants with a homogenous clinical presentation and if three or more groups are identified in the preceding work package, an analysis of variance (ANOVA) can be used. For less than three groups, an independent sample t-test will be used.

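### Section 8.3 never relates the 12-month episode counts to any movement or muscle feature, although factors for recurrence are the primary objective

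*Combined protocol and SAP*

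**What the plan says.** - **Objective.** Section 3.1: "The primary objective of this study is to identify factors responsible for recurrent shoulder instability in children". Section 8.3 opens with the same aim and says that the methods for meeting the objectives follow. Objective 3 in 8.3 reads "Categorising clinical presentations of instability and identification of important factors for recurrent instability".
- **Outcome.** The Study Summary and 3.2 list what the study will yield ("The following outcomes will be derived from this study"). The only follow-up item is "Number of recurrent episodes of instability". Section 7.8 has a diary plus monthly contact in both groups "via a telephone call for up to 12 months to record the number of instability episodes experienced".
- **Analysis.** Section 8.3 states: "The analysis of measurement units will inform the main study objective and secondary objectives". The units it lists are kinematic, kinetic and muscle-activity data from the single session. Objective 1 adds the coefficient of variation, the standard error of measurement and marker perturbation. For objective 3, "data from study objective 2 will be evaluated to identify features i.e. movement or muscle activity patterns" that may serve to categorise clinical presentations, by a clustering method to be chosen later. A conditional ANOVA covers three or more groups, and "For less than three groups, an independent sample t-test will be used".
- **Cases.** Section 6.1.1 admits first and recurrent episodes, children in current rehabilitation, and children with a further episode after surgery.

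**The concern.** The episode count is the only prospective measure of recurrence in the study, and it has no planned use in 8.3, not even a descriptive summary. What 8.3 does produce is a description of cases and controls and, possibly, clusters.

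Neither can speak to recurrence alone. A feature that separates cases from controls is associated with having an unstable shoulder. It may precede the instability, follow from it, or reflect rehabilitation or surgery. Because the cases mix first and recurrent episodes, the contrast with controls is not a contrast between children who do and do not recur.

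The risk is that such a feature is reported as *responsible* for recurrence. Section 1 intends the findings to guide exercise prescription and referral, so the wording of the conclusion matters. Thirty children are also asked for up to 12 months of diaries and calls with no stated analysis.

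**Working it through.** **1. Text check.** The documents give no power calculation or 12-month recurrence rate, so there is no figure to reproduce. Each step of 8.3 was set against the episode count:

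| Step in 8.3 | Data used | Episode count used? |
|---|---|---|
| Kinematic and kinetic summaries | Session | No |
| Muscle-activity measures | Session | No |
| Objective 1: variability, error, perturbation | Session | No |
| Objective 2 | Session, as above | No |
| Objective 3, step i | Objective 2 data | No |
| ANOVA or t-test | Groups found earlier; no outcome named | Not stated |

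No step names the count as outcome, grouping variable or summary.

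**2. What 15 cases could support.** All rates here are assumptions. The 70%-90% in sections 1 and 2 has no time window, and section 11 (Measurement burden) does not expect many episodes.

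*Any episode versus none.* With X ~ Binomial(15, p), the chance that the smaller group has 2 or fewer children is P(X ≤ 2) + P(X ≥ 13):
- p = 0.5: 2 × (1 + 15 + 105)/32,768 = 0.7%
- p = 0.3 or 0.7: 12.7%
- p = 0.9: 81.6%

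The standardised difference detectable with 80% power (two-sided 5%, one feature) is 1.66 for a 10 v 5 split and 2.30 for 13 v 2, against 1.06 for 15 cases v 15 controls.

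*Counts.* Simulation: 15 children, one standard normal feature, negative binomial counts with variance μ + aμ², a = 0.5 or 1.0, and a true rate ratio of 2 per SD. Analysis: quasi-Poisson with a log(time) offset and t on 13 df; 3,000 runs per setting. Here m is the yearly rate for a child at the average feature value. The mean across children is exp((ln 2)²/2) = 1.27 times higher. Runs with no usable fit count as not detected.

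For scale, P(any episode) = 1 − (1 + am)^(−1/a). This gives 30% at m = 0.39 (a = 0.5) or 0.43 (a = 1.0), 50% at 0.83 or 1.00, and 70% at 1.65 or 2.33.

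Power, as a = 0.5 / a = 1.0:

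| m | 12 months for all | Follow-up spread over 3-12 months |
|---|---|---|
| 0.25 | 21% / 17% | 16% / 14% |
| 0.4 | 27% / 24% | 21% / 20% |
| 0.5 | 31% / 27% | 24% / 21% |
| 1 | 46% / 36% | 35% / 30% |
| 2 | 60% / 44% | 51% / 39% |
| 4 | 70% / 49% | 63% / 45% |

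Type I error, from 1,500 runs per setting at a rate ratio of 1, was 4%-7%. Fixing m as the mean across children lowers power by 0 to 7 points. Spearman correlation had lower power in every equal-follow-up setting.

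*Precision.* The median 95% CI factor with equal follow-up runs from 1.66 to 3.72:
- Best: 2/1.66 = 1.2 to 2 × 1.66 = 3.3
- Worst: 2/3.72 = 0.5 to 2 × 3.72 = 7.4
- Worst with 3-12 months (factor 4.78): 2/4.78 = 0.4 to 2 × 4.78 = 9.6

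**3. Number of candidate features.** Section 7.6.3 has 10 sEMG sites, 7.7.2 to 7.7.4 have 3 + 1 + 3 = 7 tasks, and 8.3 names 4 muscle measures. That gives 10 × 7 × 4 = 280 muscle features. If none were related to recurrence, 280 × 0.05 = 14 would be expected to reach p < 0.05.

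**The case against.** **The ANOVA or t-test may be meant to compare episode counts between clusters.** This is the best counter-reading, since that paragraph follows the categorising step and could serve the recurrence half of objective 3. The text does not say so, and the ANOVA is conditional on a large enough homogeneous sample. If that was the intent, naming the dependent variable and stating how follow-up time is handled would close much of the gap.

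**Recurrence could be studied at baseline.** Screening (7.1.2) records initial versus recurrent episode, and 7.4 records earlier episodes. Section 8.3 links neither to any feature, and features measured after those episodes cannot be separated from their consequences.

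**The study is descriptive and small.** This stands. There is no single primary outcome, 8.1 bases the size on measurement-protocol studies, and section 11 calls reliability a primary aim. That explains the absence of a primary endpoint and limits any recurrence analysis to exploration. It does not explain leaving the outcome closest to the stated objective without any analysis.

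**The power figures rest on one effect size.** Also fair. A smaller re-run (800 runs per setting) gave about 8%-36% at a rate ratio of 1.5 and 29%-91% at 3. The finding itself depends on the text alone.

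**Conclusion.** The concern holds. Section 8.3 contains no specified step that relates later episodes to any session feature, and its only named tests have no stated outcome. As written, the study can finish without addressing its primary objective. This should be settled before analysis.

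The missing analysis would be weak: 14% to 70% power for a doubling of the rate per SD, and intervals often spanning no effect. Those figures assume 15 analysed cases, m between 0.25 and 4 per child-year, dispersion 0.5 to 1.0, one feature at a time, two-sided 5% tests without multiplicity correction, and 3 to 12 months of follow-up. They justify an exploratory label, not leaving the analysis out.

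**What to change.** Add to 8.3, under objective 3, an exploratory analysis within the instability group:

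1. Report episodes and months observed for each child. Define months observed in advance, including how a missed call followed by a later one is counted.
2. List a short, fixed number of session features before analysis. Relate each, one at a time, to the episode count by one chosen method, for example quasi-Poisson regression with a log(months) offset. State a fallback if the model cannot be fitted, such as rank correlation with the episode rate.
3. Report every listed feature with its estimate and 95% CI, with no selection by p-value and no confirmatory claim.
4. Show prior episodes, rehabilitation and surgery status descriptively alongside. Fifteen cases cannot support adjustment for all of them.
5. Summarise control-group episodes descriptively, outside this analysis.
6. Name the dependent variable of the ANOVA or t-test.
7. Describe case-control differences as associated with shoulder instability and within-case results as associated with later episodes. Call neither *responsible*.

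If this analysis is not added, reword the primary objective to match what 8.3 does.

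**Cost.** A short amendment, agreed with the sponsor and submitted by the route in section 11. No new visits or data items are needed: 7.8, 7.4 and 7.1.2 already cover the counts, history, rehabilitation and surgery, and months observed can be taken from the call record. The price is wide intervals and a more modest headline claim.
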